9.6 Data Management

The Study Site will receive data collection tools (CRFs, questionnaires) from CLINACT. Whenever possible, complete data sets should be entered. Text field entries and any data collected on paper should be legible and follow the requested language standard.

The Study Site Responsible must sign off the complete data set reported by the site for each patient, confirming the collected data. Adverse Event and Other experiences reported according to section 11 should be signed off separately by a physician involved in the study. A causality evaluation should always be provided.

Data Management will be carried out according to a Data Management Plan which will be written and approved before the design of the study database is finalized. The data management provider should approve all data formats before the data collection tools are made available to the sites.

If the written informed consent of a patient is known not to be available in spite of it being required, data for this patient is not entered into or is deleted from the database.

THIS DOCUMENT CONTAINS TRADE SECRETS, AND/OR COMMERCIAL OR FINANCIAL INFORMATION, PRIVILEGED OR CONFIDENTIAL, DELIVERED IN CONFIDENCE AND RELIANCE THAT SUCH INFORMATION WILL NOT BE COPIED OR MADE AVAILABLE TO ANY THIRD PARTY WITHOUT THE WRITTEN CONSENT OF LEO PHARMA A/S

If a patient is erroneously included in the study more than once only the data relating to the first inclusion will be kept in the database and be available for analysis. Data from later inclusions will be transferred to the first dataset when relevant, i.e. if collected within the time frame of the first follow-up period.

If a patient is included in the study in spite of not being treated according to the approved terms of the marketing authorization, data is kept in the database and analysed separately and as part of the overall analyses as described in the Statistical Analysis Plan.

LEO owns the data collected in the CRF and as PRO. General Data Protection Regulation (European Commission, 2016) (GDPR) must be adhered to, in addition to any local laws and regulations regarding data privacy. The study must follow the EFPIA HCP Code Article 15 Non-Interventional Studies of Marketed Medicines (The European Federation of Pharmaceutical Industries and Associations, 2008).

The Study Master File compiled by the CRO should be transferred to LEO affiliate when complete. The Complete Study Master File comprises both LEO and CRO compiled documents but should not hold duplicates.

The Study Database compiled by CRO should be transferred to LEO HQ when complete.

Safety data collection and reporting from this NIS must follow the current version of the EMA Guideline on Good pharmacovigilance practices (GVP) Module VI – Management and reporting of adverse reactions to medicinal products (European Medicines Agency, 2017). For reporting please refer to Section 11.

The data extracted from medical records and databases is not owned by LEO. The collection must be guided by relevant guidance documents, e.g. Guidance for Industry and FDA Staff: Best Practices for Conducting and Reporting Pharmacoepidemiologic Safety Studies Using Electronic Healthcare Data (Food and Drug Administration, 2013), the ISPOR Good Research Practice for Retrospective Database Analysis Task Force Report (Berger et al., 2009), and the European Network of Centres for Pharmacoepidemiology and Pharmacovigilance (ENCePP) Guide on Methodological Standards in Pharmacoepidemiology and Code of Conduct (European Medicines Agency, 2010).

When collecting database data, collection and submission of single case safety data is not required. For data collected from medical records, please refer to Section 11.

9.7 Data Analysis

This study is observational and epidemiological methods will be employed for data analyses. Descriptive analysis will be performed of all collected data, except data collected only for the purpose of data cleaning.

Section 9.7.1 describes the statistical analyses as foreseen at the time of planning the study. Any known deviations from the planned analyses, the reason for such deviations and all alternative/additional statistical analyses that may be performed as well as the final statistical analysis must be described in a revised Statistical Analysis Plan (SAP) before completion of data collection. All later deviations and/or alterations will be summarised in the Clinical Study Report.

9.8 Statistical Analysis Plan

Data analyses will be performed using SAS Version 9.4 or further (SAS Institute, Cary, NC USA software).

Quantitative parameters will be described using the following summary descriptive statistics: number of non-missing values, mean, standard deviation, median, first and third quartiles, and minimum and maximum values.

Qualitative parameters will be described overall using frequencies and percentages. Percentages will be calculated on the number of non-missing observations.

The level of significance for all comparisons is set at 0.05 using two-tailed tests. Confidence intervals at 95% could be provided, if relevant.

9.8.1 Description of the population

The safety population will comprise all included patients having received at least one dose of treatment.

The efficacy population will comprise all included patients who fulfill all inclusion and exclusion criteria.

The total number of patients included in the study, in each analysis population and related reasons of exclusion will be described.

The total number of patients attended each visit, number and reasons of study discontinuation will also be described.

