Assess at week 12/16, post biologic treatment, the sensitivity and the specificity, compared to DLQI as a standard tool, of the PSO-TARGET QoL component grid as a novel approach aiming to evaluate the patients' satisfaction with regard of their treatment.

THIS DOCUMENT CONTAINS TRADE SECRETS, AND/OR COMMERCIAL OR FINANCIAL INFORMATION, PRIVILEGED OR CONFIDENTIAL, DELIVERED IN CONFIDENCE AND RELIANCE THAT SUCH INFORMATION WILL NOT BE COPIED OR MADE AVAILABLE TO ANY THIRD PARTY WITHOUT THE WRITTEN CONSENT OF LEO PHARMA A/S

Secondary objectives:

- Evaluate at week 12/16, post Kyntheum® treatment, the percentage of patients who has achieved the main treatment goal they identified in the QoL component grid at baseline.
- Identification of predictive factors (among baseline characteristics) of the achievement of the main treatment goal;
- Evaluate the level of agreement between the dimensions reported by the patient and by the treating physician;
- Evaluate at 52 weeks the percentage of patients for whom the therapeutic objective initially achieved at the 1st follow-up visit is still maintained;
- Evaluate the percentage of patients who change their therapeutic objective after 12/16 weeks of treatment;
- Follow the evolution of the PASI score (at 12/16 and 52 weeks);
- Level of accordance between PASI 90/100 and the satisfaction level in regard to the therapeutic objective set by the PSO-TARGET QoL Component grid;
- Follow the evolution of the DLQI score (at 12/16 and 52 weeks).

Study design

PSO-TARGET is an observational, non-interventional, prospective, multicentric, international, European study requiring no change in the patients' standard of care (RIPH3 in France).

Population

Adult patients suffering from moderate to severe *psoriasis vulgaris* for whom the dermatologist decided to prescribe a treatment with Kyntheum®.

Variables**Primary endpoint**

- At 12/16 weeks, level of concordance between the satisfaction level in regard to the therapeutic objective set by the PSO-TARGET QoL Component grid and the DLQI in assessing the impact of the treatment on the patients' quality of life.

Secondary endpoints

- At week 12/16, post Kyntheum® treatment, the percentage of patients who achieved the main treatment goal identified by the patient himself in the QoL component grid at

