
the dermatologist symptomatic approach. We therefore believe that it is of importance to assess the 4 components of quality of life usually impacted in case of chronic disease as defined by Chassany (Chassany, 2003; Forestier et al., 2019), before initiating the systemic treatment, in order to define better therapeutics goals in an holistic approach. It is necessary to assess this new approach in a homogenous population, thus only patients starting a biologic treatment by Kyntheum® at the inclusion in the study will be enrolled. Indeed, satisfaction towards a treatment may be influenced by several factors including administration regimen.

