9.1 Study Design

9.1.1 Eligibility criteria

The inclusion criteria are the following:

- Age > 18 years

THIS DOCUMENT CONTAINS TRADE SECRETS, AND/OR COMMERCIAL OR FINANCIAL INFORMATION, PRIVILEGED OR CONFIDENTIAL, DELIVERED IN CONFIDENCE AND RELIANCE THAT SUCH INFORMATION WILL NOT BE COPIED OR MADE AVAILABLE TO ANY THIRD PARTY WITHOUT THE WRITTEN CONSENT OF LEO PHARMA A/S

- Patient for whom the dermatologist decided to initiate a treatment by Kyntheum® according to SmPC.
- Patient who signed an informed consent.

The following non-inclusion criteria will be applied:

- Vulnerable subjects according to the law;
 - pregnant, parturient or breast feeding women;
 - deprived of their freedom by administrative, medical or legal decision or who is under trusteeship/guardianship;
 - legally protected, or unable to express their consent to participate;
 - With no affiliation to a social security system;
- Psychologically/linguistically unable to express their consent to participate;
- With an hypersensitivity to at least one of the excipients of Kyntheum®;
- Participating at the same time in another clinical trial.

9.1.2 PSO-TARGET Quality of Life Component grid.

As a first step to construct the component grid, a retrospective survey based on the recollection and experience from 3 clinical dermatologists (2 French and 1 Belgian) of patient's expectations, has been conducted. The results of the survey have been used to generate a grid containing 12 therapeutic goals equally distributed into the 4 major psychometric components classically used in quality of life studies in patients suffering from chronic diseases (Chassany, 2003; Forestier et al., 2019). These four dimensions (cf table 1) are the following:

- **Physical:** autonomy, physical capabilities, ability to perform daily activities;
- **Subjective:** linked to experienced emotion, anxiety, well-being;
- **Relational/social:** with family, friendship or professional environment, engaging personal relationships, involvement in social or leisure activities;
- **Therapeutic:** linked to treatment, for ex. treatment-/care-related discomfort.

The investigators participating to the study will agree to implement this table as part of their standard of care along with the DLQI questionnaire.

Table 1: Quality of Life (QoL) component grid

Physical	Subjective	Relational/ social	Therapeutic
----------	------------	--------------------	-------------

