9.1.4 Limitation of bias

In order to limit bias, the sensitivity and specificity analysis need to be performed on a population as homogenous as possible. To this end, only patients treated with brodalumab (Kyntheum®) will be enrolled. By doing so we will limit the bias due to different treatment profiles (schedule of drug administration....). However, Kyntheum® efficacy will not be assessed during the study.

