9.8.3 Sensitivity/sensibility analysis

- Analysis of the primary endpoint

The primary endpoint will be the evaluation at week 12/16 of the sensitivity and the specificity, compared to the DLQI as a standard, of the PSO-TARGET QoL component grid to assess the level of satisfaction of patient achieving the therapeutic goal, identified by himself.

The therapeutic objective will be considered as achieved if the patient gives the responses “Satisfied” or “Very Satisfied” on the Likert scale. The response will then be compared to the DLQI score at 12/16 weeks.

It will be described on the efficacy population.

A contingency table will be constructed as follows:

PSO-TARGET \ DLQI	0-1	2-5	6-10	11-20	21-30
Very satisfied	TP	FP	FP	FP	FP
Satisfied	TP	FP	FP	FP	FP
Unsatisfied	FN	TN	TN	TN	TN
Very unsatisfied	FN	TN	TN	TN	TN

This table can be summarized as :

PSO-TARGET \ DLQI	0-1	≥ 2
Very satisfied ou Satisfied	TP	FP
Unsatisfied ou Very unsatisfied	FN	TN

TP: True positive

FP: False Positive

FN: False Negative

TN: True Negative

The validity of the QoL component grid will then be assessed by calculating the following parameters:

Sensitivity: defined as the probability to have patients who have reached their therapeutic target (who have responded « satisfied » or « very satisfied » on the Likert scale, globally and in each major domains) among patients with a DLQI score between 0 and 1.

In other terms the sensitivity is defined as the **concordance** of the QoL component grid and the DLQI **for the patients with optimal quality of life**.

The sensitivity is calculated by:

$$Se = \frac{TP}{TP + FN}$$

Specificity: defined as the probability to have patients who have not reached their therapeutic target (who have responded « unsatisfied » or « very unsatisfied » on the Likert scale, globally and in each major domains) among patients with a DLQI score ≥2.

In other terms the specificity is defined as the **concordance** of the QoL component grid and the DLQI **for the patients with suboptimal quality of life**.

The specificity is calculated by:

$$Sp = \frac{TN}{FP + TN}$$

The QoL component grid will be validated if these two parameters reach the threshold of 85%.

THIS DOCUMENT CONTAINS TRADE SECRETS, AND/OR COMMERCIAL OR FINANCIAL INFORMATION, PRIVILEGED OR CONFIDENTIAL, DELIVERED IN CONFIDENCE AND RELIANCE THAT SUCH INFORMATION WILL NOT BE COPIED OR MADE AVAILABLE TO ANY THIRD PARTY WITHOUT THE WRITTEN CONSENT OF LEO PHARMA A/S

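### The efficacy population has no dose condition, so eligible patients who consent but never start Kyntheum are counted as non-responders in the secondary goal-achievement rate

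*Protocol*

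**What the plan says.** Section 9.8.1 defines the two analysis sets in consecutive sentences. For safety: "The safety population will comprise all included patients having received at least one dose of treatment". For efficacy: "The efficacy population will comprise all included patients who fulfill all inclusion and exclusion criteria".

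Of the inclusion criteria in Section 9.1.1, only one concerns treatment: "Patient for whom the dermatologist decided to initiate a treatment by Kyntheum® according to SmPC". It asks for a decision, not for receipt. Section 9.2 equates enrolment with signing the consent form, and Sections 4 and 7 have the patient complete the grid before treatment begins. Inclusion therefore precedes the first dose.

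Other sections describe a treated cohort. Section 9.1.4, on keeping the sensitivity and specificity analysis homogeneous, says: "To this end, only patients treated with brodalumab (Kyntheum®) will be enrolled". Section 7 says: "thus only patients starting a biologic treatment by Kyntheum® at the inclusion in the study will be enrolled". The primary objective in Section 4 reads: "Assess at week 12/16, post biologic treatment, the sensitivity and the specificity". The goal-achievement objective in Section 4 is likewise placed after Kyntheum treatment.

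Two analyses on the efficacy population matter here:
- **Primary table (Section 9.8.3):** "It will be described on the efficacy population". The Likert answer is set against the DLQI: "The response will then be compared to the DLQI score at 12/16 weeks". The table has no missing category.
- **Goal achievement (Section 9.8.4, secondary):** the main analysis treats missing data as non-response. An observed-case analysis serves as the sensitivity analysis.

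**The concern.** A patient can meet every criterion in Section 9.1.1, sign consent, fill in the baseline grid and DLQI, and then never take Kyntheum. Under Section 9.8.1 this patient is left out of the safety population but kept in the efficacy population. The definition does not carry through the intent stated in Sections 4, 7 and 9.1.4.

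What is at stake differs by endpoint. In Section 9.8.4 a never-starter with no week 12/16 answer is scored as having missed a goal set for a treatment never received. This lowers a percentage that is meant to describe treated patients. In Section 9.8.3 a never-starter matters only if both week 12/16 questionnaires come back. If they do, the patient is classified by the answers given, and those answers say nothing about how the grid performs after treatment.

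**Working it through.** **Inputs from the protocol (Sections 9.5, 9.8.3).** Sensitivity 0.80 under the null and 0.90 under the alternative; alpha 0.05; power 0.80; 80% of patients with DLQI 0-1; 134 evaluable patients; 10% not evaluable; 150 included; 85% threshold for both sensitivity and specificity.

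**Assumptions not in the protocol.** The number of never-starters, k, is taken as 3 to 7 of 150 (about 2% to 5%). Goal achievement among starters is taken as 80%. Specificity among treated patients is taken as 0.80.

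**1. The plan's own figure.** An exact binomial test with 0.025 in the upper tail needs 107 patients with DLQI 0-1 (reject at 94 or more; exact alpha 0.0233; power 0.819). Then 107 / 0.80 = 133.75, rounded up to 134, which matches. 134 / 0.90 = 148.9, or 149, against the stated 150. No stated figure is wrong, and a dose condition does not alter this calculation.

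**2. Membership of the efficacy population.** Decision to initiate: met. Consent: met. Non-inclusion criteria: none apply. Dose: not asked for. The never-starter is in.

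**3. Goal achievement (Section 9.8.4).** Suppose never-starters have no week 12/16 answer and no other data are missing. The rate under the non-responder rule is 0.80 × (150 − k) / 150.
- k = 3: 0.80 × 147 / 150 = 117.6 / 150 = 78.4%
- k = 7: 0.80 × 143 / 150 = 114.4 / 150 = 76.3%

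With a dose condition the rate is 80%, so the loss is 1.6 to 3.7 points.

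**4. Primary table, no questionnaires returned (Section 9.8.3).** A cell needs an observed Likert answer and an observed DLQI. The never-starter fills no cell, and sensitivity and specificity are unchanged.

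**5. Primary table, both questionnaires returned.** As an upper bound, let all k be unsatisfied with DLQI of 2 or more, so that all are true negatives. With 134 evaluable in total and 20% of starters at DLQI of 2 or more, D = 0.20 × (134 − k), and specificity becomes (0.80 D + k) / (D + k).
- k = 3: D = 26.2; (20.96 + 3) / 29.2 = 0.821
- k = 7: D = 25.4; (20.32 + 7) / 32.4 = 0.843

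**6. Effect on the 85% decision.** At the planned prevalence about 0.20 × 134 = 26.8, or 27, patients carry specificity. With true specificity 0.80:
- 27 treated patients: 23 or more true negatives are needed, and the probability of that is 34.8%. Adding 1 to 6 never-treated true negatives leaves the requirement at 23 of the treated 27 (for example, (22 + 6) / 33 = 84.8%, still short), so the probability stays at 34.8%.
- 25 treated patients: 22 or more are needed (21/25 = 84.0% fails), with probability 23.4%. Adding one changes nothing (22/26 = 84.6%). Adding two makes 21 sufficient (23/27 = 85.2%), and the probability becomes 42.1%.

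The effect on the decision is either nil or appreciable, depending on how close the count lies to the threshold.

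**The case against.** The strongest reply is that the intent is clear. Sections 4, 7 and 9.1.4 all speak of treated or starting patients, so included patients could be read as treated patients. Section 9.1.4 also gives uniform administration schedules as its reason, not the removal of untreated patients. This makes the point a matter of aligning text, but it does not remove it: Section 9.1.5 refers to patients planned to receive Kyntheum, Section 9.2 ties enrolment to consent, and Section 9.8.1 is the operative definition.

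Second, the observed-case analysis in Section 9.8.4 already drops never-starters who are not seen. That is true, but it also drops treated patients with missing data, so it does not isolate the problem, and the non-responder analysis remains the main one. The assumed shift of 1.6 to 3.7 points is also smaller than the 95% confidence half-width of about 6.4 points (1.96 × √(0.8 × 0.2 / 150)). That limits its importance, although it is a one-directional bias that is simple to avoid.

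Third, a one-dose rule still keeps a patient who stops after one dose. That is correct, but such a patient was treated and falls within the objective.

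Fourth, the specificity route rests on untested assumptions. An untreated patient would have to attend at weeks 12-16 and rate satisfaction with a goal set for a drug not taken. That patient might also have moved to another therapy and could land in any cell. This stands, and it is why the route is given only conditional weight.

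**Conclusion.** The gap is real. As written, eligible patients who never receive Kyntheum belong to the efficacy population, against the protocol's own description of its cohort and objectives. The main consequence is a diluted secondary goal-achievement rate: about 78.4% to 76.3% in place of 80%, assuming 3 to 7 never-starters among 150, 80% achievement in starters and no week 12/16 answers from never-starters. The protocol gives no never-start rate, so this size is illustrative.

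A reader might infer that never-starters automatically enter the primary table and count there as failures. The protocol does not support that. The non-responder rule belongs to Section 9.8.4 alone; Section 9.8.3 needs both observed answers and imputes no failures. An unsatisfied never-starter with DLQI of 2 or more would be a true negative, which moves specificity up.

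A reader might also infer that each such patient steadily improves the chance of passing 85%. Fixing the group at 27 and replacing 2 or 4 treated patients with true negatives does give 42.1% and 50.1% against 34.8%, but that also shrinks the treated group. Adding never-starters to the same treated patients often changes nothing. The effect on the primary decision is conditional and minor unless the result is close to the threshold.

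**What to change.** In Section 9.8.1, define the efficacy population as included patients who fulfil all inclusion and exclusion criteria and received at least one dose of Kyntheum. List never-treated patients among the reasons for exclusion, which that section already requires to be described.

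The cost is one sentence. The date of treatment initiation is already collected (Section 9.3), so no new data are needed. The efficacy population may lose a few patients. The 134 evaluable and 150 included patients stand.

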9.8.2 Baseline characteristics

Baseline and demographic characteristics will be described on the analysis population and will be summarized using appropriate summary statistics such as mean, standard deviation, median, minimum and maximum for continuous variables, and frequency counts and percentages for categorical variables.

9.8.3 Sensitivity/sensibility analysis

- Analysis of the primary endpoint

The primary endpoint will be the evaluation at week 12/16 of the sensitivity and the specificity, compared to the DLQI as a standard, of the PSO-TARGET QoL component grid to assess the level of satisfaction of patient achieving the therapeutic goal, identified by himself.

The therapeutic objective will be considered as achieved if the patient gives the responses “Satisfied” or “Very Satisfied” on the Likert scale. The response will then be compared to the DLQI score at 12/16 weeks.

It will be described on the efficacy population.

A contingency table will be constructed as follows:

PSO-TARGET \ DLQI	0-1	2-5	6-10	11-20	21-30
Very satisfied	TP	FP	FP	FP	FP
Satisfied	TP	FP	FP	FP	FP
Unsatisfied	FN	TN	TN	TN	TN
Very unsatisfied	FN	TN	TN	TN	TN

This table can be summarized as :

PSO-TARGET \ DLQI	0-1	≥ 2
Very satisfied ou Satisfied	TP	FP
Unsatisfied ou Very unsatisfied	FN	TN

TP: True positive

FP: False Positive

FN: False Negative

TN: True Negative

The validity of the QoL component grid will then be assessed by calculating the following parameters:

Sensitivity: defined as the probability to have patients who have reached their therapeutic target (who have responded « satisfied » or « very satisfied » on the Likert scale, globally and in each major domains) among patients with a DLQI score between 0 and 1.

In other terms the sensitivity is defined as the **concordance** of the QoL component grid and the DLQI **for the patients with optimal quality of life**.

The sensitivity is calculated by:

$$Se = \frac{TP}{TP + FN}$$

Specificity: defined as the probability to have patients who have not reached their therapeutic target (who have responded « unsatisfied » or « very unsatisfied » on the Likert scale, globally and in each major domains) among patients with a DLQI score ≥2.

In other terms the specificity is defined as the **concordance** of the QoL component grid and the DLQI **for the patients with suboptimal quality of life**.

The specificity is calculated by:

$$Sp = \frac{TN}{FP + TN}$$

The QoL component grid will be validated if these two parameters reach the threshold of 85%.

THIS DOCUMENT CONTAINS TRADE SECRETS, AND/OR COMMERCIAL OR FINANCIAL INFORMATION, PRIVILEGED OR CONFIDENTIAL, DELIVERED IN CONFIDENCE AND RELIANCE THAT SUCH INFORMATION WILL NOT BE COPIED OR MADE AVAILABLE TO ANY THIRD PARTY WITHOUT THE WRITTEN CONSENT OF LEO PHARMA A/S

Objective	Statistical analysis	Exposure measure	Outcome measure	Covariates
1	Contingency table; Sensitivity / Specificity	N/A	Concordance level between PSO- TARGET Component grid and DLQI at 12/16 weeks	N/A

- Analysis of the secondary performance endpoints

Analyses of secondary endpoints will be performed on the efficacy population.

No replacement of missing data will be performed.

The same analysis as the primary performance analysis will be performed at 52 weeks.

